### **3.2.5 Bath Ankylosing Spondylitis Metrology Index (BASMI)**

The BASMI characterizes the spinal mobility of subjects with AS. The BASMI is a disease-specific measure consisting of 5 clinical measures to reflect subject axial status: cervical rotation; tragus to wall distance; lateral spinal flexion; modified Schober test; intermalleolar distance. The mean of the 5 scores provides the BASMI score. The higher the BASMI score the more severe the subject's limitation of movement due to their axSpA.

**Table 3.1: BASMI linear definition**

$S = (21.1 \text{ cm} - A) / 2.1 \text{ cm}$	For the lateral lumbar spine flexion (mean right/left)
$S = (A - 8 \text{ cm}) / 3 \text{ cm}$	For the tragus-to-wall distance (mean right/left)
$S = (7.4 \text{ cm} - A) / 0.7 \text{ cm}$	For the lumbar flexion (modified Schober)
$S = (124.5 \text{ cm} - A) / 10 \text{ cm}$	For the maximal intermalleolar distance
$S = (89.3^\circ - A) / 8.5^\circ$	For the cervical spine rotation (mean right/left)
Always with the additional condition $0 \leq S \leq 10^a$	

a S=score, A=assessment.

For cervical rotation, tragus-to-wall distance and lumbar flexion, take the mean of the left and right measurements, if both are available. Otherwise, the available measurement will be used.

With regard of the lumbar flexion (modified Schober), values greater than 9.0 cm will be flagged as invalid and treated as if they were missing values.

When calculating observed case score, if one or more clinical measures are missing at a visit, then BASMI total score will be treated as missing at that visit. No imputation will be performed.

When performing LOCF imputation, following rules will be applied:

- If up to two clinical measures are missing at a visit, the previous value(s) for the clinical measure(s) will be carried forward to replace the missing value(s), assuming the previous value(s) were from a post-baseline assessment. If there are no previous post-baseline value(s) to carry forward, then the previous visit's total BASMI score will be carried forward, assuming the previous visit was a post-baseline assessment. Otherwise the LOCF score is missing for that visit.
- If more than two clinical measures are missing at a visit, then the previous visit's total BASMI score will be carried forward, assuming the previous visit was a post-baseline assessment. Otherwise the LOCF score is missing for that visit.

### 3.2.6 Total and nocturnal spinal pain NRS

Total and nocturnal spinal pain scores are based on following NRS:

- Pain in the spine due to AS (ie, “How much pain of your spine due to spondylitis do you have?”)
- Pain in the spine at night due to AS (ie, “How much pain of your spine due to spondylitis do you have at night?”).

The scores range from 0 to 10, with lower scores indicating less pain.

### 3.2.7 Ankylosing Spondylitis Disease Activity Score (ASDAS)

The ASDAS is comprised of a number of assessments which are scored by the subject and physician and multiplied by a proven formula as listed:

$0.121 \times$  Back pain (BASDAI Q2 result, see Section 3.2.1)

$0.058 \times$  Duration of morning stiffness (BASDAI Q6 result)

$0.110 \times$  PtGADA (see Section 3.2.10)

$0.073 \times$  Peripheral pain/swelling (BASDAI Q3 result)

$0.579 \times$  (natural logarithm of the (CRP [mg/L] + 1))

Back pain, PtGADA, duration of morning stiffness and peripheral pain/swelling are all assessed on an NRS (0 to 10 units). If the CRP value is below the LLOQ, then it will be imputed as the midpoint between 0 and the LLOQ.

For Part A Baseline derivation of the ASDAS score the latest value prior to treatment will be used for each component. It will be not required that all components are measured at the same visit, e.g. PtGADA is available only at screening while the other components are available at Baseline then the ASDAS score will be derived combining the screening value of PtGADA and the baseline value of the other components.

For Part B Baseline derivation of the ASDAS score the latest value prior to randomization will be used for each component. It will be not required that all components are measured at the same visit.

For Flare Baseline derivation of the ASDAS score the latest value prior to first injection in Escape Part will be used for each component. It will be not required that all components are measured at the same visit.

When calculating observed case score, if one or more components are missing at a visit, then ASDAS will be treated as missing at that visit. No imputation will be performed.

When performing LOCF imputation, following rules will be applied:

- If only one component is missing at a visit, the previous value for that one component only will be carried forward to replace the missing value, assuming the previous value was a post-baseline assessment, and will be used to calculate the ASDAS score. If there is no previous post-baseline value available for that one component to carry forward, the previous visit's total ASDAS score will be carried forward, assuming the previous visit was a post-baseline assessment. Otherwise the LOCF score is missing at that visit.
- If more than one component is missing at a visit, the previous visit's total ASDAS score will be carried forward, assuming the previous visit was a post-baseline assessment. Otherwise the LOCF score is missing at that visit.

Disease activity is measured by binary response variables derived from ASDAS as follows:

- ASDAS-Inactive Disease (ASDAS-ID): ASDAS  $<1.3$
- ASDAS-Low Disease activity (ASDAS-LD): ASDAS  $\geq 1.3, < 2.1$
- ASDAS-High Disease activity (ASDAS-HD): ASDAS  $\geq 2.1, \leq 3.5$
- ASDAS-very High Disease activity (ASDAS-vHD): ASDAS  $> 3.5$

ASDAS improvement is measured by binary response variables defined as follows:

[figure not shown]
- ASDAS-CII: ASDAS reduction (improvement) of  $\geq 1.1$  relative to Baseline
- ASDAS-MI: ASDAS reduction (improvement) of  $\geq 2.0$  relative to Baseline. As a sensitivity analysis, ASDAS-MI analyses will be repeated using a Modified ASDAS-MI: ASDAS reduction (improvement) of  $\geq 2.0$  relative to Baseline or has the lowest score possible post-baseline (i.e. when CRP<LLOQ and all other components are 0, then the minimum ASDAS score is 0.636 to 3 decimal places).

[figure not shown]
### **3.2.8 Ankylosing Spondylitis Quality of Life (ASQoL)**

The ASQoL, a validated disease-specific 18-item questionnaire, has been recently developed specifically for measuring health-related quality of life (HRQoL) in subjects with AS. The ASQoL has been used and has shown to be responsive in axSpA. The ASQoL score ranges from 0 to 18 with higher score indicating worse HRQoL.

If three or less items responses are missing, the ASQoL score will be imputed by dividing the sum score with the number of available responses and multiplying the result with 18. If more than three items responses are missing, the ASQoL score will be left missing.

### **3.2.9 Work Productivity Survey (WPS)**

hereof.

### **3.2.10        Patient's Global Assessment of Disease Activity (PtGADA, NRS)**

Subjects will score their global assessment of their disease activity in response to the question “How active was your spondylitis on average during the last week?” using a NRS where 0 is “not active” and 10 is “very active”.

### 3.2.11 Short-Form 36-item Health Survey (SF-36)

The SF-36 (Version 2, standard recall) is a 36 item generic HRQoL instrument that uses a recall period of 4 weeks. Items are grouped into 8 domains as follows: Physical Functioning (10 items), Role Physical (4 items), Bodily Pain (2 items), General Health (5 items), Vitality (4 items), Social Functioning (2 items), Role Emotional (3 items), Mental Health (5 items), and a further unscaled single item (Q2) for perceived stability or change in health (Health Transition) during the last year. The concepts represented by these domains contribute to physical, mental, and social aspects of HRQoL.

For the calculation of the SF-36 domain scores and the component summaries PCS and MCS, the scoring software Optum's PRO CoRE will be used. The norm-based scores (based on the US 2009 general population) will be utilized for analysis.

A response definition for the PCS and MCS is based on the within-subject MCID of 2.5 points. A subject will be considered a PCS (MCS) responder if the subject has an increase of  $\geq 2.5$  points from Baseline.

### 3.2.12 Maastricht Ankylosing Spondylitis Enthesitis Score (MASES)

The MASES comprises 13 items (bilateral costochondral 1, costochondral 7, anterior superior iliac spine, posterior iliac spine, iliac crest and proximal insertion of the Achilles tendon sites, and the fifth lumbar vertebral body spinous process) (Heuft-Dorenbosch et al, 2003) each scored as 0 = yes or 1 = no and then summed for a possible score of 0 to 13, with higher scores indicating worse enthesitis.

If 7 or more items are available, MASES will be imputed by dividing the sum score with the number of assessments and multiplying the result with 13. If less than 7 items are available, MASES will be treated as missing.

### 3.2.13 Swollen and Tender Joint Counts (44)

Tender and swollen joint counts will be carried out on the following 44 joints:

- Upper body (4) – bilateral sternoclavicular, and acromioclavicular joints
- Upper extremity (26) – bilateral shoulders, elbows, wrists (includes radiocarpal, carpal and carpometacarpal bones considered as a single unit), metacarpophalangeals (MCPs) I, II, III, IV, and V, and thumb interphalangeals (IPs), and proximal IPs (PIPs) II, III, IV, and V
- Lower extremity (14) – bilateral knees, ankles, and metatarsophalangeals (I, II, III, IV, and V)

The assessment for swelling and tenderness is made on the 44 joints from the above list and ranges from 0 to 44. Artificial, ankylosed, and missing joints are excluded from swelling and tenderness assessments.

Each joint is scored as follows:

**Table 3.2: Tender and swollen joint scoring**

Grade	Swelling response (44)	Tenderness response (44)
0	None	None
1	Swelling present	Tenderness present

If there are missing observations for tender or swollen joints then the remaining observations will be assessed and weighted by dividing by number of non-missing and by multiplying by 44 for the joint count. If a joint is not evaluable at Baseline, then that joint is set to missing throughout the study.

If data for more than 50% of the joints are missing at the time of a given assessment, then no imputation will be done, and the total count will be set to missing for that visit.

### **3.2.14 Physician's Global Assessment of Disease Activity (PhGADA)**

The Investigator will assess the overall status of the subject with respect to the axSpA signs and symptoms and the functional capacity of the subject using a VAS where 0 is “very good, asymptomatic and no limitation of normal activities” and 100 is “very poor, very severe symptoms which are intolerable and inability to carry out all normal activities.”

This assessment by the Investigator should be made without any knowledge of the PtGADA.

### **3.2.15 Spinal mobility**

In addition to the assessments performed for the BASMI, additional spinal mobility assessments include:

- Occiput to wall distance
- Chest expansion

### **3.2.16 Health status (EQ-5D-3L)**

The EQ-5D-3L is comprised of a 5-item health status measures and a VAS. Each of the 5 health states is divided into 3 levels: no problem, some or moderate problems and extreme problems and is scored as 1, 2, and 3, respectively. The EQ-5D-3L VAS records the respondent's self-rated health status on a vertical 20cm scale, 0 to 100 graduated (0=worst imaginable health status, 100=best imaginable health status).

This instrument is to be completed by the subject.

### **3.2.17 Resource utilization**

The following resource utilization data will be collected through UCB standardized modules:

- Concomitant medical procedures
- Health care provider consultations not foreseen by the protocol
- In-patient hospitalizations and emergency room visits (including length of stay)

A medical resource will be allocated to Part A as determined by the (start) date of the event.

Specifically, a medical resource will be allocated to Part A if (start) date is on or after the date of first study medication in Part A and prior to or on the date of last study medication in Part A + 70 days and prior to the date of first study medication in Part B, if any.

A medical resource will be allocated to Part B as determined by the (start) date of the event.

Specifically, a medical resource will be allocated to Part B if (start) date is on or after the date of first study medication in Part B and prior to or on the date of last study medication in Part B + 70 days. Medical resource with a (start) date after date of first escape full-dose CZP injection will be excluded from any summary tables of medical resource in Part B.

A medical resource will be allocated to Part B post-flare as determined by the (start) date of the event. Specifically, a medical resource will be allocated to Part B post-flare if (start) date is on or after the date of first escape full-dose CZP injection in Part B and prior to or on the date of last escape full-dose CZP injection in Part B + 70 days.

The same rules for (partially) missing start dates as for AEs will be applied to the resource use data.

For the same subject only one hospitalization will be considered if “start date of the second hospitalization - end date of the first hospitalization  $\leq 1$ ”.

In case of complete consultation date, count only once for a same subject, same consultation date, same location and same provider.

If the procedure name, start date and relationship are the same, then only one procedure is counted, otherwise if at least one variable among procedure name, start date or relationship is different, distinct/several procedures are counted.

If concomitant medical procedures, health care provider consultations not foreseen by the protocol, and in-patient hospitalizations and emergency room visits are not available during Part A, Part B and Part B post-flare the respective number variable will be set to 0.

See Section 12.1.2 for specific counting rules for the resource utilization.

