#### **2.3.3 Escape treatment**

Subjects experiencing a flare in Part B will be invited for an on-site visit to receive the next planned dose of investigational product (escape treatment). This visit will take place 2 weeks after the last assessment that resulted in meeting the flare criteria; or, at the discretion of the Investigator, at an earlier time point. As the start of escape treatment may vary from subject to subject, it will be referred to as “Escape Week 0”. Subjects will remain on the escape treatment for at least 12 weeks or until Week 96 of the regular visit schedule as described in Table 5.1 in the protocol, whichever is longer.

The assessment-schedule for subjects experiencing a flare in Part B will start 2 weeks after the flare condition is fulfilled; or, at the discretion of the Investigator, at an earlier time point and will end 2 weeks before Week 96 after Baseline of the regular assessment schedule. If the flare occurs late in Part B (at or after Week 82), the subject must receive the escape treatment for 12 weeks (eg, starting at Week 84 until Week 96). The final assessments at study end (as laid down for Week 96) must be performed 2 weeks after the last study dose administration accordingly.

Subjects receiving PBO or half-dose CZP (200mg Q4W) who experience a flare during the Double-Blind Period will escape to full-dose treatment (CZP 200mg Q2W) until the end of that period or for at least 12 weeks, whichever is longer. The escapers need to come back to the site at the time point of the escape (Week 0), 2 and 4 weeks after escape (Weeks 2 and 4), and every 12 weeks thereafter until the originally scheduled Week 96.

Subjects escaping from PBO to full-dose CZP (200mg Q2W) will receive a loading dose of CZP (400mg Q2W) at the 3 consecutive visits after the flare. Subjects escaping from half-dose CZP to full-dose CZP will receive CZP 200mg Q2W at the 3 consecutive visits after the flare. In order to maintain the blind, subjects escaping from half-dose CZP to full-dose CZP will receive a PBO-administration and a CZP 200mg administration at these 3 visits.

Subjects randomized to the CZP full-dose (200mg Q2W) treatment during the Double-Blind Period who qualify for escape will remain on their current treatment allocation. As with subjects escaping from half-dose CZP to full-dose CZP, these subjects will receive a PBO and CZP 200mg injection at the 3 visits after the flare in order to maintain the blind to the randomized treatment.

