#### **2.3.4 Study duration per subject**

For each subject, there is a planned duration of up to 109 weeks, as follows:

- Up to 5 weeks of Screening Period
- 48 weeks in the Open-Label Period
- 48 weeks in the Double-Blind Period

- An SFU Visit 10 weeks after last dose administration (Period 4).

Of note, the last dosing in the Double-Blind Period occurs at Week 94 so that the SFU of 10 weeks already includes 2 weeks from the Double-Blind Period hence leading to a duration of 109 weeks.

Subjects in UK will be contacted by a telephone call 22 weeks after the last dose of their study medication hence leading to a duration of 121 weeks.

For subjects who experience a flare during the Double-Blind Period, the study duration might be prolonged.

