### **8.3.1.23 Resources utilization**

Summary statistics and frequency distribution (number of subjects by number of medical resources used) will be presented by axSpA subpopulation and all subjects for concomitant medical procedures, health care provider consultations, and in-patient hospitalizations and emergency room visits, including length of stay. These summaries will be produced for the OLS using observed case data.

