### **8.3.2.9 Number of uveitis flares, IBD exacerbations and psoriasis exacerbations**

Separate tables will be produced to summarize incidence of each of these events (uveitis flares, IBD exacerbations and psoriasis exacerbations) during Part B.

These summary tables will display the number and percentage of subjects experiencing the considered event in Part B, number of event, incidence rate, event rate and 100 patient exposure year. Only the events occurring up to Escape Week 0 will be considered. In this style of output, “number of event” will include all occurrences of the event including repeat occurrences in individual subjects, while “number of subjects” will count each subject only once.

The presentation will be performed by treatment group using observed case data.

For each of these events (uveitis flares, IBD exacerbations and psoriasis exacerbations), the summary table will be repeated based on the subset of subjects with a history of occurrence and/or a current occurrence of the event at screening.

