### 8.3.2.12 Descriptive summaries of other efficacy variables

The below listed efficacy variables will be summarized descriptively by visit and by treatment group as applicable using observed case based on the RS unless otherwise specified.

- ASDAS disease activity (ASDAS-ID, ASDAS-LD, ASDAS-HD and ASDAS-vHD)
- Change from Part A Baseline and change from Part B Baseline in SIJ SPARCC and spine ASspiMRI-a in the Berlin modification scores (summaries based on observed case data only)
- Change from Part A Baseline and change from Part B Baseline in PhGADA
- Change from Part A Baseline and change from Part B Baseline in nocturnal spinal pain (NRS)
- CRP (actual values, change from Part A Baseline values, change from Part B Baseline values, ratio of post-Baseline over Part A Baseline values, ratio of post-Baseline over Part B Baseline values)
- Health status as assessed by the EQ-5D-3L: domains, VAS actual score, change from Part A Baseline and change from Part B Baseline in VAS score
- Change from Part A Baseline and change from Part B Baseline in MASES
- Change from Part A Baseline and change from Part B Baseline in swollen and tender joint counts (44 joint counts). The summaries for TJC will be repeated including only the subjects with a TJC>0 at Part A Baseline or Part B Baseline, as appropriate. Similar approach will be used for SJC.
- Change from Part A Baseline and change from Part B Baseline in spinal mobility as assessed by occiput to wall distance and in spinal mobility as assessed by chest expansion
- Change from Part A Baseline and change from Part B Baseline in fecal calprotectin (summaries based on observed case data only)
- Change from Part A Baseline and change from Part B Baseline in serum calprotectin (summaries based on observed case data only)
- Change from Part A Baseline and change from Part B Baseline in the IBD-Q scores (Global IBD-Q total score, IBD-Q bowel symptoms score, IBD-Q systemic symptoms score, IBD-Q emotional function score and IBD-Q social function score)
- Frequency of IBD-Q responders and IBD-Q remitters (NRI data will be used) using Part A Baseline and Part B Baseline as reference
- Resources utilization: concomitant medical procedures, healthcare provider consultations not foreseen by the protocol, in-patient hospitalizations and emergency room visits

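### Part B resource use is summarised by arm with no time denominator, although follow-up stops at escape and is therefore shorter on placebo

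*SAP*

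**What the plan says.** Direct medical resource utilization is one of the other objectives in SAP Section 2.1.3. Section 3.2.17 sets the counting rules:

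- A resource belongs to Part B if it starts on or after the first Part B dose and "prior to or on the date of last study medication in Part B + 70 days".
- For escapers, anything with a start "date after date of first escape full-dose CZP injection will be excluded from any summary tables of medical resource in Part B".
- Resources from the first escape injection onwards go to a separate post-flare allocation.
- A subject with no record in a period is given a count of 0.

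Section 8.3.2.12 then lists "Resources utilization: concomitant medical procedures, healthcare provider consultations not foreseen by the protocol, in-patient hospitalizations and emergency room visits" among the variables summarised descriptively by visit and treatment group on observed cases. The only table format given anywhere is for Part A (8.3.1.23): "Summary statistics and frequency distribution (number of subjects by number of medical resources used"). Post-escape use is summarised under 8.3.3, on the Flared Set and by randomized arm, also without a time denominator.

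For uveitis, IBD and psoriasis events in Part B, which are also counted only up to Escape Week 0, Section 8.3.2.9 asks for "number of event, incidence rate, event rate and 100 patient exposure year".

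**The concern.** How long a subject contributes to the Part B resource table depends on whether that subject escapes. A subject who never escapes is counted to the end of the window. A subject who escapes is counted only until the first escape injection, and the zero rule treats a short window without events the same as a long one. The trial expects far more flares on placebo than on full-dose CZP, so equal true use per unit of time would appear as fewer resources per subject on placebo. At stake is the descriptive comparison for a stated objective: resource use under withdrawal would be understated relative to continued treatment, by an amount that grows with the flare difference the trial is designed to show.

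**Working it through.** The SAP gives no figure for observed time by arm, so there is none to reproduce. The flare-free proportions used below come from Section 2.4. There they reproduce the stated power of 98% and 94% to within about a percentage point (Fisher exact 98.9% and 94.0%; continuity-corrected 98.8% and 93.9%; 70 per arm, two-sided 0.05).

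**Inputs from the SAP**
- Flare-free proportion p: 0.80 (Q2W), 0.75 (Q4W), 0.45 (placebo), Section 2.4.
- Window for a non-escaper: "the last dosing in the Double-Blind Period occurs at Week 94" (Section 2.3.4), which is 46 weeks after the Week 48 dose. Adding 70 days (10 weeks) gives W = 56 weeks.
- Lag from flare to escape, Section 2.3.3: "This visit will take place 2 weeks after the last assessment that resulted in meeting the flare criteria", or earlier at the investigator's discretion. Taken as 2 weeks.

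**Assumptions not in the SAP**
- Every flare leads to escape.
- Flare times are exponential over 48 weeks with S(48) = p. As alternatives, mean flare time is set between 8 and 36 weeks, and W to 48 weeks (counting to Week 96 only).

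**Central case.** E[T] = p × W + ∫₀⁴⁸ (t + 2) f(t) dt. With λ = −ln(p)/48, the integral is (1 − p)/λ − 48p + 2(1 − p).
- Placebo: λ = 0.01664. The integral is 33.06 − 21.6 + 1.1 ≈ 12.6. E[T] = 25.2 + 12.6 ≈ 37.8 weeks.
- Q2W: λ = 0.00465. The integral is 43.02 − 38.4 + 0.4 ≈ 5.0. E[T] = 44.8 + 5.0 ≈ 49.8 weeks.
- Q4W, by the same steps: 48.2 weeks.

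Per 70 subjects this is 50.7 (placebo), 66.8 (Q2W) and 64.7 (Q4W) patient-years. Placebo/Q2W = 0.76, a 24% shortfall. Q4W/Q2W = 0.97, so the two CZP arms are little affected relative to each other.

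**Range.** With a common mean escape time e (mean flare time + 2), E[T] = p × W + (1 − p) × e.

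| W (weeks) | e (weeks) | Placebo | Q2W | Ratio | Shortfall |
|---|---|---|---|---|---|
| 56 | 10 | 30.7 | 46.8 | 0.66 | 34% |
| 56 | 26 | 39.5 | 50.0 | 0.79 | 21% |
| 56 | 38 | 46.1 | 52.4 | 0.88 | 12% |
| 48 | 26 | 35.9 | 43.6 | 0.82 | 18% |
| 48 | 38 | 42.5 | 46.0 | 0.92 | 8% |

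**Break-even.** Counts per subject are equal when the true placebo/Q2W rate ratio is the inverse of the time ratio. That is about 1.32 in the central case (49.8/37.8), with a range of 1.08 to 1.52. Below that value placebo shows the lower count; above it, the higher one.

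**The case against.** The case against has several parts.

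- **The denominator exists.** Section 10.1.2.1 derives patient time at risk from the Week 48 injection to the last Part B injection plus 70 days, censored at the start of escape, and summarises patient-years by treatment group. That is essentially the resource window. This stands, but it makes the fix cheap rather than unnecessary. Those totals sit in a safety table on the Safety Set Part B by actual treatment, whereas the efficacy tables use the Randomized Set as randomized.
- **Post-escape use is not lost.** It is tabulated under 8.3.3. This stands. However, that table covers the Flared Set only and has no denominator. An event on the day of the first escape injection also falls in both tables, because Part B excludes only later dates while the post-flare allocation includes that day.
- **The cut at escape is the SAP's general convention for Part B.** This stands, and the cut is not the defect. A total over all of Part B answers a different question and is a supplement, not a correction.
- **The Part B table format is not spelled out, so rates are not excluded.** This is true, but a rate is specified for the comparable events in 8.3.2.9 and not here.
- **Not every flare is an escape.** Section 3.2.22 counts any premature withdrawal as a flare, and a subject who withdraws without escaping is counted to last dose plus 70 days. This stands as a limit on the size. If such withdrawals were equally frequent and equally timed in both arms, the absolute gap under a common mean escape time, 0.35 × (W − e), would not change. If they were unequal, it would.

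A reader might go further and infer that withdrawal will look cheaper than it is, or that the objective will be answered in the wrong direction. The SAP does not support either inference. It plans no cost analysis and no test of resource use, and it gives no resource rates. Care around the flare itself can also fall before escape, which could raise the placebo rate within the window.

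**Conclusion.** The point holds as a missing time denominator. Under the SAP's own flare-free assumptions, and if every flare leads to escape, placebo is observed for about 24% less time than Q2W, with a range of roughly 8% to 34% over the flare timings and windows tried. By-arm counts per subject therefore understate placebo use relative to CZP. The direction of that distortion is the same in every case computed. Its size rests on assumptions about flare timing and escape that the SAP does not settle, and a reversed ranking cannot be claimed without the true rates. Severity is minor: this is a descriptive other variable, and the primary analysis, multiplicity and sample size are unaffected.

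**What to change.** In Sections 8.3.2.12 and 8.3.3, state that each resource category will be shown by arm as number of events, patient-years in the allocation window, and events per 100 patient-years, as in 8.3.2.9. Use the individual time at risk already derived in 10.1.2.1 (before escape) and 10.1.2.2 (after escape), summed by randomized arm so that numerator and denominator cover the same subjects. A Flared Set subject with no escape dose adds no post-escape time.

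As an optional supplement, add one descriptive table of all Part B resource use by randomized arm, including use after escape, with an event dated on the first escape injection day counted once.

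The cost is SAP wording, a little programming and some table space. No new data are needed.
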